10.4 Expedited Adverse Event Reporting Requirements for IND/IDE Agents

10.41 Phase 1 and Early Phase 2 Studies: Expedited Reporting via the **ACCRU Adverse Event Expedited Report Form** for Adverse Events That Occur Within 30 Days¹ of the Last Dose of the Investigational Agent

FDA REPORTING REQUIREMENTS FOR SERIOUS ADVERSE EVENTS (21 CFR Part 312) NOTE: Investigators MUST immediately report to the sponsor ANY Serious Adverse Events, whether or not they are considered related to the investigational agent(s)/intervention (21 CFR 312.64) An adverse event is considered serious if it results in ANY of the following outcomes:
 
 1) Death 2) A life-threatening adverse event 3) An adverse event that results in inpatient hospitalization or prolongation of existing hospitalization for \geq 24 hours 4) A persistent or significant incapacity or substantial disruption of the ability to conduct normal life functions 5) A congenital anomaly/birth defect. 6) Important Medical Events (IME) that may not result in death, be life threatening, or require hospitalization may be considered serious when, based upon medical judgment, they may jeopardize the patient or subject and may require medical or surgical intervention to prevent one of the outcomes listed in this definition. (FDA, 21 CFR 312.32; ICH E2A and ICH E6). 		

ALL SERIOUS adverse events that meet the above criteria MUST be immediately reported to the sponsor within the timeframes detailed in the table below.
		
Hospitalization	Grade 1 and Grade 2 Timeframes	Grade 3-5 Timeframes
Resulting in Hospitalization \geq 24 hrs	7 Calendar Days	24-Hour / 3 Calendar Days
Not resulting in Hospitalization \geq 24 hrs	Not required	

Expedited AE reporting timelines are defined as:
 
 o "24-Hour / 3 Calendar Days" - The AE must initially be reported within 24 hours of learning of the AE, followed by a complete expedited report within 3 calendar days of the initial 24-hour report. o "7 Calendar Days" - A complete expedited report on the AE must be submitted within 7 calendar days of learning of the AE. 		

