10.52 Baseline and Adverse Events Evaluations

Pre-treatment symptoms/conditions to be graded at baseline and adverse events to be graded at each evaluation. (Grading is not necessary in the absence of these conditions.) This list includes but is not limited to the symptoms/conditions listed below. The CTCAE v4.0 grading should be used:

System Organ Class (SOC)	Adverse event/Symptoms	Baseline	Each evaluation
Generalized	Fatigue	X	X
Gastrointestinal	Diarrhea	X	X
Cardiovascular	Hypertension	X	X
Renal	Proteinuria	X	X
Generalized	Weight loss	X	X
Renal	Acute kidney injury	X	X
Pulmonary	Pneumonitis	X	X

10.53 **Case Report Forms** - Academic and Community Cancer Research United (ACCRU) Submit the following AEs not specified in Section 10.5 (paper or electronic, as applicable).

10.54 Submit via appropriate Academic and Community Cancer Research United (ACCRU) Case Report Forms (i.e., paper or electronic, as applicable) the following AEs experienced by a patient and not specified in Section 10.5:

10.531 Grade 1 and 2 AEs deemed *possibly, probably, or definitely* related to the study treatment or procedure.

10.532 Grade 3 and 4 AEs regardless of attribution to the study treatment or procedure

10.533 Grade 5 AEs (Deaths)

10.5331 Any death within 30 days of the patient's last study treatment or procedure regardless of attribution to the study treatment or procedure.

10.5332 Any death more than 30 days after the patient's last study treatment or procedure that is felt to be at least possibly treatment related must also be submitted as a Grade 5 AE, with a CTCAE type and attribution assigned.

10.55 Refer to the instructions in the Forms Packet (or electronic data entry screens, as applicable) regarding the submission of late occurring AEs following completion of the Active Monitoring Phase (i.e., compliance with Test Schedule in Section 4.0).

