16.2 Sample Size/Accrual Rate

16.21 Sample Size: A total of 25 evaluable Cohort 1 and 25 evaluable Cohort 2 patients will be accrued per study design (50 evaluable total), unless one or both cohorts of the study are permanently closed at the stage 1 analysis or undue

toxicity is observed. We anticipate accruing an additional 10 patients (5 Cohort 1, 5 Cohort 2) in order to account for ineligibility, cancellation, major treatment violation, or other reasons. Therefore, maximum accrual is 60 patients for this trial (30 for each Cohort).

16.22 Accrual Time and Study Duration: We expect to accrue about 3 patients per month to this trial. Therefore, the accrual period for this Phase II study is expected to be about 20 months. We anticipate that the study will take approximately 3 years to complete. This allows a 6 month follow-up for the final patient enrolled, along with data entry, data clean-up, and analysis.

16.3 Analysis of Secondary Endpoints for both Cohorts.

This study will assess multiple secondary endpoints, including adverse events, progression-free survival (PFS) and overall survival (OS). All these analyses will be done for each cohort separately. In addition, all primary/secondary data will be summarized by descriptive factors as well (i.e. prior treatment, etc.).

16.31 Adverse Events: All patients that have initiated treatment will be considered evaluable for assessing adverse events. The maximum grade for each type of adverse event will be recorded for each patient, and frequency tables will be reviewed to determine adverse event patterns. Only the grade 2+ adverse events will be assessed, regardless of relationship to the study treatment.

16.32 Progression-Free Survival (PFS): Defined as the time from registration to the first of either death due to any cause or progression. The distribution of PFS will be estimated using the method of Kaplan-Meier.

16.33 Overall Survival: Defined as the time from registration to death due to any cause. The distribution of survival time will be estimated using the method of Kaplan-Meier. Special attention will be paid to any registered patient who dies early (i.e., within 60 days) of initiating their treatment. Circumstances surrounding such early deaths will be classified as being either due to malignant disease, toxicity, other causes, or of unknown reasons.

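### Section 16.31 promises grade 2+ adverse event tables whatever the attribution, but 10.531 collects unsolicited grade 2 events mostly only when judged related

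*Combined protocol and SAP*

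**What the plan says.** Section 16.31 takes each patient's maximum grade for each type of event, by cohort, and limits the analysis by grade but not by attribution: "Only the grade 2+ adverse events will be assessed, regardless of relationship to the study treatment".

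Collection is set in 10.52 to 10.54. Section 10.52 names seven terms: fatigue, diarrhea, hypertension, proteinuria, weight loss, acute kidney injury and pneumonitis. Its instruction is "Pre-treatment symptoms/conditions to be graded at baseline and adverse events to be graded at each evaluation", with no condition on attribution, and it adds "This list includes but is not limited to the symptoms/conditions listed below".

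For everything else, 10.54 tells sites to submit "the following AEs experienced by a patient and not specified in Section 10.5". The items under it are:
- Item 10.531 sets a condition for the lower grades, and its wording is "Grade 1 and 2 AEs deemed *possibly, probably, or definitely* related to the study treatment or procedure". Attribution therefore decides whether such an event is sent in.
- Item 10.532 sets no such condition for the higher grades, and its wording is "Grade 3 and 4 AEs regardless of attribution to the study treatment or procedure".
- 10.5331 and 10.5332: deaths within 30 days of the last study treatment or procedure whatever the attribution; a later death only if one "that is felt to be at least possibly treatment related must also be submitted as a Grade 5 AE"

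Read literally, 10.531 to 10.533 are themselves part of Section 10.5. I take the exclusion in 10.54 to mean the 10.52 list, which is the only reading that gives it content.

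**The concern.** A table can be all-cause only if events are collected without regard to cause. Here the attribution condition is applied at the site, before data entry, and it applies to grades 1 and 2 but not to grades 3 and 4. An analyst following 16.31 would apply no attribution filter and could reasonably describe the result as all-cause. For unsolicited terms at grade 2, that description would be wrong, and nothing in 16.31 warns of it.

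The safety profile of the combination is secondary objective 2.21. No cohort has a concurrent control, so attribution is a matter of judgment and readers will lean on all-cause rates. A row whose grade 2 part is mostly related-only, next to solicited rows with no such condition, invites false comparisons between terms.

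**Working it through.** The plan gives no figure on this point, so the check sets the passages side by side.

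**Step 1. What 16.31 needs against what 10.54 delivers, for events outside the 10.52 list.**

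| Event | In scope of 16.31 | Submitted under 10.54 |
|---|---|---|
| Grade 2, at least possibly related | Yes | Yes (10.531) |
| Grade 2, unlikely or unrelated | Yes | No, unless another route applies |
| Grade 3-4, any attribution | Yes | Yes (10.532) |
| Grade 5 within 30 days, any attribution | Yes | Yes (10.5331) |
| Grade 5 after 30 days, unlikely or unrelated | Yes | No (10.5332) |

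The second line is the conflict. The last line needs only a footnote.

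**Step 2. Other routes for unrelated grade 2 events.** Item g of 10.1 sends every expedited report to the routine forms as well, so two routes remain open.
- *Serious events.* The opening of Section 10.0 asks sites to report all serious events whatever the attribution. Section 10.41 likewise requires "ANY Serious Adverse Events, whether or not they are considered related to the investigational agent(s)/intervention", and its definition of serious includes incapacity and important medical events without hospitalization. Its timeframe table, however, requires no report for grade 1-2 events without a hospital stay of at least 24 hours. The documents therefore state the scope of this route in two ways. More than 30 days after the last dose, its footnote asks for at least possible attribution.
- *Events of Clinical Interest (10.56).* These are reported whether or not related, but the list is short: pembrolizumab overdose without symptoms or laboratory changes, and one defined pattern of liver tests.

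On either reading of the serious-event rule, an unsolicited, non-serious, unrelated grade 2 event that is not an Event of Clinical Interest has no route onto the forms. Second malignancies and pregnancy outcomes have their own rules and are set aside here.

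**Step 3. Passages that might close the gap.**
- The note under table 8.2 asks for all grades to be collected. It is silent on attribution and sits under a table of lenvatinib-related toxicities.
- Section 10.32 says its expected events still need routine reporting, but it refers the reader to Section 10.5, where the condition sits.
- The 10.52 list is open but names no further term.

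None of these plainly requires unrelated grade 2 events to be submitted.

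**Step 4. Direction and size.** Let p be the share of patients whose maximum grade for an unsolicited term is 2, counting all causes. Let u be the fraction of those patients whose grade 2 events are all unrelated and reach the forms by no other route. The recorded share is p × (1 − u), so any error is downward. The documents give neither p nor u. As an illustration only, assume p = 20% in 25 patients (5 expected). Then u = 10%, 30% and 50% give recorded shares of 18%, 14% and 10% (4.5, 3.5 and 2.5 patients). These are assumptions that show the mechanism, not estimates.

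On breadth, 10.32 prints 18 expected terms and 10.52 prints 7. Five are on both lists (fatigue, diarrhea, weight loss, proteinuria, hypertension), so 18 − 5 = 13 expected terms are not named as solicited. This compares printed lists only. It does not count the terms affected, because the content of the solicited form listed in 18.1 is not shown.

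**Step 5. Reach.** The 16.52 rule uses grade 4 and grade 5 events that are at least possibly related, and all of these are submitted. The primary endpoints are tumor responses. Neither depends on the 10.531 condition.

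**The case against.** The strongest reply is that 16.31 prescribes no table heading. It may mean only that no further attribution filter is applied to whatever was collected. That reading is possible. Even so, the reported grade 2 results would be described as assessed whatever the attribution, and a reader could not tell which rows are complete.

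A second reply is that collection may be wider than 10.531 suggests. Section 10.32 could be read as a free-standing instruction to report its terms routinely, the 10.52 list is open, and the form could carry more terms. This stands in part: it limits confidence and leaves the number of affected terms unknown. It does not remove the conflict for a term that is not on the form.

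A third reply is that the loss may be small. Under 10.3, possible attribution requires only that the event may be related, and many of the expected terms are known toxicities of the two drugs. This also stands. A reader might infer that grade 2 rates will be badly understated, and the documents do not support that.

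A reader might also infer a baseline error: that a maximum-grade table would count a grade 2 condition already present at entry and unchanged since. The documents do not support calling this an error. Section 10.52 separates pre-treatment conditions from adverse events, 18.1 gives baseline its own form, and exclusion 3.29e limits entry with unresolved effects of earlier treatment. At most, the rule for using baseline grades is unstated.

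**Conclusion.** The conflict is real, because the analysis stated in 16.31 cannot be delivered at grade 2 for unsolicited terms from the data that 10.531 collects. It would be too strong to say that no unrelated grade 2 events are collected, since two routes remain, or that all 13 terms above are affected. Any error is downward and of unknown size. Grade 3-4 results are sound.

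Severity is minor: only the descriptive safety tables for objective 2.21 are affected. Confidence is moderate. The conclusion rests on reading the 10.54 exclusion as the 10.52 list, on reading 10.32 as subject to the 10.531 condition, and on at least some unsolicited terms not being on a form that the documents do not show.

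**What to change.** Reword 16.31 to report, by cohort and with the maximum grade taken within each table's own set of events:
1. Grade 3+ whatever the attribution, for all terms, with a footnote that grade 5 follows 10.5331 and 10.5332.
2. Grade 2+ at least possibly related, for all terms, labelled so.
3. Grade 2+ whatever the attribution, only for terms actually solicited on the form at each evaluation.

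State in one place how the note under table 8.2 and the routine-reporting line in 10.32 relate to 10.531. Optionally, add that solicited terms count when new or worse than baseline.

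The change is to analysis wording. Table 2 needs attribution for solicited terms too, and 10.1 item d already has relatedness determined for events. The content of the solicited form should be checked before the term list for table 3 is fixed. No new data collection is needed and nothing changes for patients. The downside is that all-cause grade 2 rates are not reported for unsolicited terms. Obtaining those would mean widening 10.531, which is a change in collection rather than wording.

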Phase II study of lenvatinib in radioiodine-refractory DTC led to the SELECT trial, a global, placebo-controlled randomized phase III trial of lenvatinib in radioiodine-refractory progressive DTC. The primary endpoint was PFS, which was significantly prolonged with lenvatinib versus placebo (median 18.3 months versus 3.6 months, respectively; hazard ratio [HR] 0.21; 99% confidence interval 0.14–0.31, $P < 0.001$). Lenvatinib PFS benefit was observed in all predefined subgroups, including patients who received 0 ($n=299$) or 1 ($n=93$) prior tyrosine-kinase inhibitor therapies (HR: 0.20 and 0.22, respectively). Lenvatinib significantly improved ORR versus placebo (64.8% [4 complete; 165 partial responses] versus 1.5%; $P < 0.001$). Median overall survival has not been reached. For lenvatinib, treatment-related adverse effects (>40%, all grades) were hypertension (67.8%), diarrhea (59.4%), fatigue/asthenia (59.0%), decreased appetite (50.2%), decreased weight (46.4%), and nausea (41.0%); adverse effects were managed with dose reductions and standard interventions. Discontinuations due to adverse effects occurred in 37 (14.2%) lenvatinib-treated and 3 (2.3%) placebo-treated patients. In the lenvatinib arm, 6/20 treatment-emergent deaths were considered drug-related.

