2.2 Secondary

- 2.21 To determine the safety profile and toxicity of combination therapy with pembrolizumab and lenvatinib in patients with progressive DTC. (Cohort 1 and Cohort 2)
- 2.22 To determine progression-free survival (PFS) and overall survival (OS). (Cohort 1 and Cohort 2)

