Each participating ACCRU treating location will be responsible for monitoring the supply of pembrolizumab and will use the Drug Order Request Form to order additional supplies as needed.

NOTE: in order to obtain a drug re-supply, Merck should be notified six months prior to study drug expiry.

Outdated or remaining drug is to be destroyed on-site as per procedures in place at each institution.

15.29 Nursing Guidelines:

15.291 Pembrolizumab side effects vary greatly from those of traditional chemotherapy and can vary in severity from mild to life threatening. Instruct patients to report any side effects to the study team immediately. Side effects may be immediate or delayed up to months after discontinuation of therapy. Most side effects are reversible with prompt intervention of corticosteroids.

- 15.292 Diarrhea can be seen, however, it is less common than what is seen with anti-CTLA-4 agents. It can occasionally be severe, leading to colonic perforation. Instruct patients to report ANY increase in the number of stools and/or change in baseline, blood in the stool, abdominal pain to the study team immediately.
- 15.293 Rash/pruritus/dermatitis is seen. Patients should report any rash to the study team. Treat per section 9.0 and monitor for effectiveness.
- 15.294 Monitor LFT's closely as elevations in these levels could indicate early onset autoimmune hepatitis. Patients should also be instructed to report any jaundice, or right upper quadrant pain to the study team immediately.
- 15.295 Pneumonitis can be seen and may be mild (only seen on imaging) to severe. Patients should be instructed to report any shortness of breath, dyspnea, cough, and/or chest pain to the study team immediately. Patients reporting these symptoms should have a pulse oximetry checked and consider immediate imaging per the treating physician.
- 15.296 Endocrinopathies (including hypopituitarism, hypothyroidism, hypophysitis, and adrenal insufficiency) are seen with this agent. Patients may present only with the vague sense of fatigue and "not feeling well." Additional symptoms may be that of nausea, sweating and decreased activity tolerance. Instruct patients to report these signs or symptoms immediately and obtain appropriate labs as ordered by the treating physician.

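### Section 16.31 leaves every grade 1 adverse event out of the planned safety analysis, although related and solicited grade 1 events are already collected and one of them can interrupt dosing

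*Combined protocol and SAP*

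**What the plan says.** Section 16.31 defines the adverse-event analysis. Every patient who starts treatment is evaluable. "The maximum grade for each type of adverse event will be recorded for each patient", and frequency tables are then reviewed. The section closes with the restriction: "Only the grade 2+ adverse events will be assessed", whatever their attribution. No reason is given for the grade cut.

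The secondary goal that this analysis serves is Section 2.21: "To determine the safety profile and toxicity of combination therapy with pembrolizumab and lenvatinib in patients with progressive DTC". It applies to both cohorts and sets no grade limit.

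Collection is wider than the analysis at grade 1:

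- Section 10.531 requests "Grade 1 and 2 AEs deemed *possibly, probably, or definitely* related to the study treatment or procedure".
- Section 10.52 lists seven terms (fatigue, diarrhea, hypertension, proteinuria, weight loss, acute kidney injury, pneumonitis) to be graded at baseline and at each evaluation. Section 18.1 has a form for solicited events.
- A note under the Section 8.2 table asks sites to collect all grades.

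The Section 8.3 table withholds pembrolizumab for myocarditis of grade 1 or 2. Section 1.6 gives the lenvatinib-alone background: "treatment-related adverse effects (>40%, all grades) were hypertension (67.8%), diarrhea (59.4"%), with four further effects down to nausea at 41.0%.

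**The concern.** The plan collects grade 1 information, treats at least one grade 1 event as serious enough to interrupt dosing, and then gives grade 1 events no place in the analysis meant to describe the toxicity of the combination. A patient whose pembrolizumab was withheld for grade 1 myocarditis would appear in no table produced under Section 16.31.

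The second issue is context. In a trial without a control arm, readers will look to outside figures. The event-specific lenvatinib rates in Section 1.6 cover all grades and only treatment-related events. The planned table covers grade 2 and above and any attribution. The two differ in both respects, in opposite directions, so neither can be read against the other. Section 15.192 itself raises the possibility that diarrhea is more frequent when lenvatinib is given with immunotherapy, so the question is not idle.

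**Working it through.** Section 16.31 states no figure that depends on the grade cut, so the main check is textual.

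**Step 1: collection against analysis.**

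| Event | Requested on the forms | In the 16.31 analysis |
|---|---|---|
| Grade 1, related | Yes (10.531) | No |
| Grade 1, solicited term | Yes, graded at each evaluation (10.52) | No |
| Grade 2, related or solicited | Yes (10.531, 10.52) | Yes |
| Grade 2, unrelated and unsolicited | Not under 10.531; the 8.2 note could be read to include it | Promised |
| Grade 3-4, any attribution | Yes (10.532) | Yes |
| Death within 30 days, any attribution | Yes (10.5331) | Yes |

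There are two mismatches. Grade 1 events are collected and not analysed. Unrelated, unsolicited grade 2 events are promised in the analysis but not requested by Section 10.531, so the planned table may be incomplete at grade 2.

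**Step 2: are the Section 1.6 rates usable as context?** The 37 discontinuations reported as 14.2% imply 37 / 0.142 = 260.6, or about 261 lenvatinib patients. Then 0.594 x 261 = 155.0 and 0.678 x 261 = 177.0, which are whole counts, so the rates are internally consistent. Four of the six quoted effects (hypertension, diarrhea, fatigue, weight loss) are solicited terms in Section 10.52.

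**Step 3: what the grade cut could do.** Let s be the share of affected patients whose worst grade is 1. The documents do not give s, so 10% to 60% is an assumption. The related grade 2+ rate is the all-grade rate x (1 - s).

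| All-grade related rate | s = 10% | s = 20% | s = 40% | s = 60% |
|---|---|---|---|---|
| Hypertension 67.8% | 61.0% | 54.2% | 40.7% | 27.1% |
| Diarrhea 59.4% | 53.5% | 47.5% | 35.6% | 23.8% |
| Nausea 41.0% | 36.9% | 32.8% | 24.6% | 16.4% |

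For diarrhea the drop runs from 59.4 - 53.5 = 5.9 points to 59.4 - 23.8 = 35.6 points. For scale, the 95% half-width at n = 25 is 1.96 x sqrt(0.594 x 0.406 / 25) = 19.3 points, and 17.6 points at n = 30.

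This does not reproduce the rate that Section 16.31 would print. That table also counts unrelated grade 2+ events, which push the rate up by an amount the documents do not let us estimate.

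**Step 4: how often the myocarditis case could arise.** Section 15.27 lists myocarditis with pembrolizumab at 0.1% to below 1%. In 60 patients that is 60 x 0.001 = 0.06 to 60 x 0.01 = 0.6 expected cases of any grade. The chance of at least one is 1 - 0.999^60 = 6% to 1 - 0.99^60 = 45%. Grade 1 cases would be only a part of these.

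**The case against.** The strongest reply is that nothing is lost. Related grade 1 events are on the case report forms, pneumonitis is graded at every evaluation, and Section 18.1 has a form for dose modifications, omissions and delays. Section 16.51 has the study team and the data safety monitoring board review safety at least twice a year, with no grade floor. That stands. A reader might infer that these events go unreported altogether; the documents support only that one planned analysis omits them.

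Second, no comparison of adverse-event rates with lenvatinib alone is planned; the historical hypothesis in Section 1.7 concerns complete response. Matching grades would also not make the populations alike. Section 1.8 ties the 24 mg lenvatinib dose to the phase III trial and sets 20 mg for Cohort 1. Cohort 2 stays on its current dose, which may already have been reduced, and excludes patients who stopped lenvatinib for toxicity (3.22). This stands too. A reader might infer that the plan will make the combination look safer than it is. That would require someone to ignore the grade and attribution labels, and the net direction is unknown.

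Third, imaging-only pneumonitis is a tempting example, because Section 15.295 says "Pneumonitis can be seen and may be mild (only seen on imaging) to severe". That passage assigns no grade, and the pneumonitis hold in the Section 8.3 table starts at grade 2. The inference that such cases are grade 1 and wholly omitted is not established by the documents. The myocarditis example does not depend on it.

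What the reply leaves standing is that the analysis section excludes, without a reason, data that the protocol collects and in one instance acts on.

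**Conclusion.** The point holds as a modest gap in the planned safety reporting. The grade 1 exclusion, the collection of related and solicited grade 1 events, the unrestricted safety goal and the grade 1 myocarditis hold are all explicit in the text. So is the mismatch in grade and attribution with Section 1.6. The mismatch concerns the planned table, not the data: all-grade treatment-related rates can be produced from what is already collected.

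The size of any distortion is unknown. The 6 to 36 point range for diarrhea rests on an assumed grade 1 share and describes a treatment-related rate, so it shows only that the cut could matter on the scale of sampling error. It should not be quoted as an expected bias. Myocarditis is rare enough that a case may never occur here. Primary endpoints, power, significance levels and the grade 4 and 5 stopping rules are untouched.

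**What to change.** Keep the existing any-attribution table in Section 16.31 and add to it:

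1. A table of maximum grade per patient and event type for treatment-related events of all grades, with grade 2+ and grade 3+ subtotals. This matches Section 10.531 and puts the summary on the same grade and attribution basis as the rates in Section 1.6.
2. A listing of every adverse event that led to a dose hold, whatever its grade, drawn from the adverse-event and dose-modification forms.
3. A sentence reconciling grade 2 attribution with Section 10.531 and the note under Section 8.2. Without new collection, this means stating that grade 2 events outside the solicited list are covered only when judged related.

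The new table should not replace the current sentence. A table limited to treatment-related events would drop grade 3-4 events and early deaths judged unrelated, which Sections 10.532 and 10.5331 collect for good reason in an uncontrolled trial.

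The cost is a few sentences, one table and one listing from data already on the forms. The form fields are not shown, so holds may have to be matched to events by date. No dosing rule changes.
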